### 9.2.1 Screening (Days -28 to Day -1)

- Review of all Inclusion and Exclusion Criteria
- Complete medical/medication history including:
  - 2016 WHO criteria for PMF (Section 16.2), or IWG-MRT recommended criteria for PPV-MF (Section 16.3) or PET-MF (Section 16.4).
  - Risk determination, using the IWG prognostic factors
  - Calculate ECOG performance status (Section 16.6)
  - History of all treatments for their current disease (including clinical course with ruxolitinib and/or other MF therapy) or any previous oncologic conditions; including chemical, surgical and/or radiotherapeutic
  - All concomitant medication, in addition to any used in the 15 days prior to Screening
  - Transfusion history, including: each RBC transfusion received with approximate volume and total units transfused over the 6 month period prior to Screening

**Note:** while on-study, any blood product transfusion received (RBC, platelets, etc.), with approximate volumes, and total units transfused will also be documented.

- Full PE, including Vital Signs – review of all body systems as indicated by signs/symptoms
- Height (without shoes)
- Full Local Laboratory Assessment

**Note:** In Italy, HIV, HBsAg, HBsAb, HBcAb and HCV testing must also be performed.

- Urinalysis

**Note:** If Screening/Baseline **are not** occurring on the same day, then please refer to Section 9.2.2. If Screening/Baseline **are** occurring on the same day, then the following are required at Screening:

- Germline sample(s) for Central Laboratory genomic analysis
- Blood samples for Central Laboratory genomic analysis\*
- Bone Marrow Sampling\*
- Schedule MRI or CT (if patient is not a candidate for MRI) for pre-dose Day 0 ± 2 days
- Provide patient with multiple copies of the MPN-SAF TSS **24-HOUR RECALL** tool and instruct patient to complete the questionnaire daily for 7 consecutive days beginning on Day -6 and ending pre-dose Day 0.

\*If possible, bone marrow and blood sampling for genomic analysis should be performed on the same day.

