‡Transfusion dependency before study enrollment is defined as transfusions of at least 6 units of packed red blood cells (PRBC), in the 12 weeks prior to study enrollment, for a haemoglobin level of < 85 g/L, in the absence of bleeding or treatment-induced anaemia. In addition, the most recent transfusion episode must have occurred in the 28 days prior to study enrollment. Response in transfusion-dependent patients requires absence of any PRBC transfusions during any consecutive “rolling” 12-week interval during the treatment phase, capped by a haemoglobin level of ≥ 85 g/L.

\*\*Spleen response must be confirmed by imaging studies where a  $\geq 35\%$  reduction in spleen volume, as assessed by MRI or CT, is required. Furthermore, a  $\geq 35\%$  volume reduction in the spleen, by MRI or CT, constitutes a response regardless of what is reported with physical examination.

††Symptoms are evaluated by the MPN-SAF TSS. The MPN-SAF TSS is assessed by the patients themselves and includes fatigue, concentration, early satiety, inactivity, night sweats, itching, bone pain, abdominal discomfort, weight loss, and fevers. Scoring is from 0 (absent/as good as it can be) to 10 (worst imaginable/as bad as it can be) for each item. The MPN-SAF TSS is the summation of all the individual scores (0-100 scale). Symptoms response requires  $\geq 50\%$  reduction in the MPN-SAF TSS.

‡‡Progressive disease assignment for splenomegaly requires confirmation by MRI or computed tomography showing a  $\geq 25\%$  increase in spleen volume from baseline. Baseline values for both physical examination and imaging studies refer to pretreatment baseline and not to post-treatment measurements.

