Prior medication is defined as any medication with a stop date prior to the date of first dose of IMG-7289. Concomitant medications are defined as medications or therapies with a start date on or after the first dose of IMG-7289. Medications may be flagged as both prior and concomitant if the start date is prior to the date of the first dose of IMG-7289 and the medication continued after the first dose of IMG-7289. The medications will be coded using the most updated version of WHO Drug at the time of study initiation (up-versioning will not occur) and will be listed by cohort and by patient. The number (%) of patients using prior, prior and concomitant, and concomitant medications will be summarized.

G. Prior and Concomitant Transfusions

Prior transfusions are defined as those with a transfusion start date from the 15 days prior to Screening up to the first IMG-7289 dose. Concomitant transfusions are defined as those with a transfusion start date on or after the date of the first IMG-7289 dose. Prior and concomitant transfusions will be listed and summarized.

H. Prior and Concurrent Cancer Chemotherapy

Prior chemotherapy is defined as therapy that has ended before the first IMG-7289 dose. Concurrent cancer chemotherapy is defined as having a cancer chemotherapy start date on or after the date of the first IMG-7289 dose. Prior and concurrent chemotherapy will be listed.

X. Pharmacokinetic Analyses

Pharmacokinetic data are not within the scope of this SAP. Analysis details are provided in the protocol and in a separate Pharmacokinetic Analysis Plan.

XI. References

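### SAP IX.G counts prior transfusions only from 15 days before Screening, so the summary truncates the 6-month RBC history that the protocol collects and uses a window that differs between patients

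*SAP*

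**What the plan says.** SAP section IX.G (Prior and Concomitant Transfusions) sets the rule: "Prior transfusions are defined as those with a transfusion start date from the 15 days prior to Screening up to the first IMG-7289 dose". Transfusions starting on or after the first dose are concomitant. The section ends: "Prior and concomitant transfusions will be listed and summarized".

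Protocol section 9.2.1 (Screening) asks for a transfusion history covering "each RBC transfusion received with approximate volume and total units transfused over the 6 month period prior to Screening". In the same list, the 15-day period belongs to medication: "All concomitant medication, in addition to any used in the 15 days prior to Screening". A note there adds that transfusions of any blood product are documented while the patient is on study.

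Protocol section 16.7 (response criteria) defines baseline transfusion dependency as "transfusions of at least 6 units of packed red blood cells (PRBC), in the 12 weeks prior to study enrollment", for haemoglobin below 85 g/L and without bleeding or treatment-induced anaemia. It adds that "the most recent transfusion episode must have occurred in the 28 days prior to study enrollment".

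Two other SAP provisions bear on this. Section VI.D does not permit partial transfusion start dates. Section VI.M says listings cover all recorded data unless stated otherwise.

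**The concern.** The SAP rule is much shorter than both the collection period and the dependency look-back. Read literally, an RBC transfusion given 16 or more days before Screening is neither prior nor concomitant, so it has no place in the IX.G summary although the site recorded it. The neighbouring SAP definitions of prior medication (IX.F) and prior chemotherapy (IX.H) have no such lower date limit. The window also ends at first dose but starts relative to Screening, so its length depends on how long each patient spent in Screening.

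Anaemia is an expected pharmacodynamic effect of the drug (protocol section 8.2.1), and transfusions are allowed throughout dosing. Readers will look at this summary to see whether transfusion need rose or fell. A short, uneven period before treatment, set beside a treatment period of 169 days or more in Phase 2b, cannot answer that from raw counts.

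**Working it through.** The plan gives no figure to reproduce, so the check is arithmetic on the windows.

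**Inputs**
- SAP look-back before Screening: 15 days (SAP IX.G).
- Screening to Day 0, called s: at most 28 days (protocol 9.2.1), or at most 21 days if Screening and Baseline are one visit (protocol 9.2).
- Smallest practical s: 6 days. The 24-hour symptom forms are handed out at the Screening or Baseline visit for daily completion from Day -6 (protocol 9.2.1 and 9.2.2), so Screening cannot follow Day -6.
- Dependency look-back: 12 weeks = 84 days, threshold 6 units (protocol 16.7).
- Collection period: 6 months before Screening, taken as 26 weeks = 182 days (assumption).
- Enrolment is approximated by Day 0 (assumption). It favours the SAP: earlier enrolment moves the 84 days further back, so less of them is covered.

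**Window length**

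SAP window = 15 + s. Share of the dependency look-back = (15 + s)/84. Expected units at the threshold rate, evenly spread = 6 × (15 + s)/84.

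| Screening on | SAP window | Share of 84 days | Units shown |
|---|---|---|---|
| Day -6 | 15 + 6 = 21 days | 21/84 = 25% | 6 × 21/84 = 1.5 |
| Day -21 | 15 + 21 = 36 days | 36/84 = 43% | 6 × 36/84 = 2.6 |
| Day -28 | 15 + 28 = 43 days | 43/84 = 51% | 6 × 43/84 = 3.1 |

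The window never reaches 84 days. The longest is 43/21 = 2.0 times the shortest. If s is below 13, the window is shorter than the 28 days of the recency condition (15 + 13 = 28).

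**Against what is collected**

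Collected period before first dose = 182 + s, that is 188 to 210 days. The SAP window is 21/188 = 11% to 43/210 = 20% of it. The collected period contains the full 84 days for every patient.

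**Lumpy transfusions**

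Suppose a patient receives 2 units every 28 days, which is 6 units in any 84 days. In a 21-day window, 21 of the 28 possible timings show 2 units and 7 show none. In a 43-day window, 15 of 28 timings show 4 units and 13 show 2. Neither ever shows 6.

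**Against the treatment period**

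At an unchanged rate of 6 units per 84 days, the 169-day Initial Treatment Period would hold 6 × 169/84 = 12.1 units, against 1.5 to 3.1 shown as prior. Raw counts would differ by a factor of 169/43 = 3.9 to 169/21 = 8.0 with no change in transfusion need.

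**The case against.** The strongest reply is that IX.G is a descriptive safety section that states no before-and-after contrast and no test. A label deletes nothing: the records remain in the database with complete start dates, and the general listing rule in SAP VI.M could still show them. That stands. What is shown is a truncated prior category in the summary, not lost data.

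A reader might infer that anaemia response will be misclassified. The documents do not support that. No readable text links the prior label to dependency or response, and the SAP contents on disease history and on efficacy after spleen size are redacted; a proper 12-week derivation may sit there. Nor is dependency the whole denominator for anaemia response: transfusion-independent patients with baseline haemoglobin below 100 g/L are also eligible, so dependency defines one stratum.

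A reader might also take Screening on Day -1 and put the shortest window at 16 days. The symptom-form schedule rules that out; about 21 days is the practical minimum.

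Three further limits stand:
- The truncation affects counts and units. With evenly spread transfusions, a rate per week would not be biased, though a 21-day window would estimate it poorly.
- The 6-month history covers RBC only. No 6-month platelet history is required, so one longer window for all products would mix unequal collection.
- The SAP also covers 18 Phase 1/2a patients treated under earlier protocol versions, whose collection period is not visible.

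That the 15 days were carried over from the medication bullet is plausible but remains conjecture.

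None of this reconciles the two documents. No readable passage gives a reason for a 15-day transfusion window.

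**Conclusion.** The point holds for RBC transfusions in the IX.G summary. Followed as written, the rule covers about 21 to 43 days before first dose, or 25% to 51% of the dependency look-back and about 11% to 20% of the collected history. The length varies about two-fold between patients. A patient at the dependency threshold would show roughly 1.5 to 3.1 units instead of 6, so raw counts do not describe baseline RBC burden and cannot be set against on-treatment counts.

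These figures assume Screening between Day -28 and Day -6, even spacing of transfusions, 6 months taken as 182 days, and enrolment close to Day 0. They apply to patients whose history was taken under the current protocol section 9.2.1.

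Severity is minor to moderate. The primary spleen-volume analysis is not affected, haematologic response is an exploratory objective, and an effect on anaemia response is possible but not demonstrated.

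**What to change.** In SAP IX.G:

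1. Define prior RBC transfusions as those starting from 6 months before Screening up to first dose, or within a fixed 12 weeks before first dose. Apply this to patients whose history was collected under that rule.
2. Report RBC units per 4 weeks before and during treatment: 28 × units / days in the period.
3. State a separate window for platelets and other products, and for Phase 1/2a patients if their collection differed.
4. Derive baseline transfusion dependency from all the conditions in protocol section 16.7 (units in 12 weeks, haemoglobin, absence of bleeding or treatment-induced anaemia, and recency), not from the prior flag. If this is already done elsewhere in the SAP, cross-refer to it.

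The cost is SAP wording and minor programming. No new data are needed for patients whose RBC history was taken under the current protocol; for Phase 1/2a patients, check first what was collected.
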